4.7. Rationale for Correlative Testing

We will assess the expression level of PD-1, PD-L1 and PD-L2 and Tumor Infiltrating Lymphocytes (TIL) content in tumor samples and its correlation with response to investigational therapy. Initial studies suggest that baseline PD-L1 tumor cell expression

could serve as a key biomarker for response to PD-1 pathway inhibition. Tumor PD-L1 upregulation has been the factor most strongly correlated with response to PD-1 blockade. Biopsy specimen analysis will endeavor to serve this question in HGNETs. We will utilize archived tumor tissue to perform the analysis and patients without available archived tissue; may undergo an optional fresh biopsy at enrollment. Tumor infiltrating lymphocytes (TILs) will be evaluated by H&E immunohistochemical staining. Guided by our preliminary work (section 4.4-study rationale)[45], mutational analysis of tumors using next gen sequencing platform will be conducted to identify predictive biomarkers and guide future therapy beyond checkpoint inhibitors.

Additionally, using peripheral blood samples, we will assess PD-1 expression and leukocyte activation markers on circulating lymphocytes as well as NK- and T-cell function pretreatment, during treatment as well as at time of progression in order to assess potential associations with treatment response and outcome. Preliminary studies of immune cell biomarkers, including PD-1, on peripheral blood mononuclear cells in renal cell carcinoma by our group have indicated that PD-1 expression on fresh peripheral blood leukocytes may provide a useful marker for disease progression. Furthermore, the results suggest that measuring PD-1 levels in peripheral blood may assist in identifying patients likely to respond to PD-1 blocking antibodies.

5.0 Study Plan

5.1. Description of Study Design, Population and Duration of Study Therapy

This is a single arm phase II study of pembrolizumab in patients with metastatic high grade neuroendocrine carcinoma (except small cell and merkel cell carcinoma) who have failed therapy with a platinum agent. Objective response rate will be measured with disease imaging following every 3 cycles for the first year and then every 4 cycles. Patients will continue treatment until disease progression, unacceptable toxicity or for a total of 35 cycles. Overall survival will be assessed every 12 weeks during long term follow up.

Patient Selection Inclusion & Exclusion

5.2. Inclusion Criteria

- 5.2.1. Patients must have histologically or cytologically confirmed metastatic, high grade NET (Ki67 >20%), excluding any high grade NETs of large or small cell type of lung/thymus origin and merkel cell carcinoma
- 5.2.2. Patients must have measurable disease, defined as at least one lesion that can be accurately measured in at least one dimension in accordance with RECIST criteria v. 1.1 as described in detail in section 12.0
- 5.2.3. Has received prior therapy with at least 1 platinum-containing regimen
- 5.2.4. Age \geq 18 years.
- 5.2.5. ECOG performance status 0 or 1 Copyright© 2016 Fox Chase Cancer Center® Clinical Trials Operations. All rights reserved. Version Date 03/03/17

5.2.6. Patients must have normal organ and marrow function as defined below in table 1

Table 1: Adequate Organ Function Laboratory Values

System	Laboratory Value
Hematological	
Absolute neutrophil count (ANC)	≥1,500 /mcL
Platelets	≥100,000 / mcL
Hemoglobin	\geq 8 g/dL or \geq 5.6 mmol/L without transfusion or EPO dependency (within 7 days of assessment)
Renal	
Serum creatinine OR	≤1.5 X upper limit of normal (ULN) OR
Measured or calculated ^a creatinine	
clearance	\geq 50 mL/min for subject with creatinine levels > 1.5 X
(GFR can also be used in place of	institutional ULN
creatinine or CrCl)	
Hepatic	
Serum total bilirubin	≤ 1.5 X ULN OR
	Direct bilirubin \leq ULN for subjects with total bilirubin levels $>$

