8.5.4. Second Course Phase (Retreatment Period)

Subjects who stop pembrolizumab with SD or better may be eligible for up to 18 cycles of additional pembrolizumab therapy if they progress after stopping study treatment. This retreatment is termed the Second Course Phase of this study and is only available if the study remains open and the subject meets the following conditions:

Either

- Stopped initial treatment with pembrolizumab after attaining an investigatordetermined confirmed CR according to RECIST 1.1, and
- Was treated for at least 24 weeks with pembrolizumab before discontinuing therapy
- Received at least two treatments with pembrolizumab beyond the date when the initial CR was declared

OR

• Had SD, PR or CR and stopped pembrolizumab treatment after 35 cycles of study therapy for reasons other than disease progression or intolerability

AND

- Experienced an investigator-determined confirmed radiographic disease progression after stopping their initial treatment with pembrolizumab
- Did not receive any anti-cancer treatment since the last dose of pembrolizumab
- Has a performance status of 0 or 1 on the ECOG Performance Scale
- Demonstrates adequate organ function as detailed in Section 6.1
- Female subject of childbearing potential should have a negative serum pregnancy test within 72 hours prior to receiving retreatment with study medication.
- Female subject of childbearing potential should be willing to use 2 methods of birth control or be surgically sterile, or abstain from heterosexual activity for the course of the study through 120 days after the last dose of study medication (Section 6.5.2). Subjects of child bearing potential are those who have not been surgically sterilized or have been free from menses for > 1 year.
- Male subject should agree to use an adequate method of contraception starting with the first dose of study therapy through 120 days after the last dose of study therapy.
- Does not have a history or current evidence of any condition, therapy, or laboratory abnormality that might interfere with the subject's participation for the full duration of the trial or is not in the best interest of the subject to participate, in the opinion of the treating investigator.

Subjects who restart treatment will be retreated at the same dose and dose interval as when they last received pembrolizumab. Treatment will be administered for up to 18 additional cycles.

Visit requirements are outlined in Section 10.0 – study calendar.

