13.0 Statistical Considerations

13.1. Study Design/Endpoints

The primary objective will be measured by the primary endpoint of Objective Response Rate (per RECIST 1.1) among all treated subjects. Secondary endpoints include PFS (per RECIST 1.1) and OS. As discussed in the background, no second line treatments have been studied prospectively for high grade neuroendocrine carcinomas and small retrospective studies have shown dismal results with chemotherapy[11-13]. Hence we decided to proceed with a single stage statistical design given minimal if any, harm associated with ineffective therapy to study participants.

A proportion of patients with favorable response less than 5.0% will be of no interest. The investigational agent would be of interest if the ORR is at least 20.0%. Estimates are based on historical controls from published data {Hentic, 2012 #70;Olsen, 2012 #71;{Sorbye, 2013 #36}. Only those patients who have measurable disease present at baseline, have received at least one cycle of therapy, and have had their disease re-evaluated will be considered evaluable for response. (Note: Patients who exhibit objective disease progression prior to the end of cycle 1 will also be considered evaluable.) Patients who are not evaluable for response will be replaced. However, all patients who received at least 1 dose of the study drug will be included in the safety analysis. Twenty-one patients would be needed to test the null hypothesis: $p \le 0.05$ against the alternative hypothesis: $p \ge 0.20$ at the 8.5% level of significance and with 82.1% power. After 21 patients are evaluated if 3 or more patients with favorable response are observed then the null hypothesis is rejected.

Early stopping rules for safety/adverse events:

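### Two limits in eligibility Table 1 (5.2.6) are wrong as written: the paired hemoglobin values are not equivalent, and the albumin unit makes that criterion exclude nobody

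*Combined protocol and SAP*

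**What the plan says.** Section 5.2.6 is a mandatory inclusion criterion: "Patients must have normal organ and marrow function as defined below in table 1". Two rows of that table matter here.

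- **Hemoglobin:** at least 8 g/dL, joined by *or* to at least "5.6 mmol/L without transfusion or EPO dependency (within 7 days of assessment".
- **Albumin:** at least 2.5 mg/dL.

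No other section repeats, corrects or explains either limit. Table 4 in 8.3 lists both as tests, without limits or units. Section 5.5 requires a completed eligibility checklist before registration.

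Organ function is required again for the Second Course. Section 8.5.4 words it as "Demonstrates adequate organ function as detailed in Section 6.1". Section 6.1 is the one-row trial treatment table and holds no laboratory values. Section 6.7, on stopping after a complete response, instead refers retreated patients to the safety parameters in the inclusion and exclusion criteria.

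**The concern.** A limit given in two units should be one limit. Here the g/dL and mmol/L figures look too far apart for rounding to explain, so at least one of them is not what was meant. The albumin figure is in a unit three orders of magnitude smaller than the one in which serum albumin is normally expressed, which suggests that the criterion does no work.

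Consistent and intended eligibility is at stake. These are pass/fail thresholds for entry, and a checklist copied from Table 1 carries both faults to every participating site. At retreatment, a reader who follows the reference in 8.5.4 finds no thresholds.

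**Working it through.** **Inputs.** From Table 1: hemoglobin 8 g/dL and 5.6 mmol/L; albumin 2.5 mg/dL. The documents give no conversion factor, so the hemoglobin molar mass M is an assumption: about 16.1 g/mmol for the monomer, varied from 16.0 to 16.5.

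**Hemoglobin.** Formulas: mmol/L = (g/dL × 10) / M, and g/dL = mmol/L × M / 10. Trying first to reproduce the stated pairing:

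| M (g/mmol) | 8 g/dL in mmol/L | 5.6 mmol/L in g/dL | Gap in g/dL |
|---|---|---|---|
| 16.0 | 80/16.0 = 5.00 | 5.6 × 1.60 = 8.96 | 0.96 |
| 16.1 | 80/16.1 = 4.97 | 5.6 × 1.61 = 9.02 | 1.02 |
| 16.5 | 80/16.5 = 4.85 | 5.6 × 1.65 = 9.24 | 1.24 |

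The pairing is not reproduced. It would need M = 80/5.6 = 14.3 g/mmol, outside the range. The tetramer mass (about 64.5 g/mmol) does not rescue it: 80/64.5 = 1.24 mmol/L, and 5.6 × 6.45 = 36.1 g/dL.

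Example: 8.5 g/dL is 85/16.1 = 5.28 mmol/L (5.15 to 5.31 over the range). That patient meets the g/dL half and fails the mmol/L half. Because the halves are joined by *or*, meeting one is enough, so on a literal reading the patient is eligible.

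**Albumin.** 2.5 mg/dL / 1000 = 0.0025 g/dL. A very low albumin of 1.0 g/dL is 1000 mg/dL, and 1000/2.5 = 400 times the written limit. If g/dL was the intended unit, the written limit is 2.5/0.0025 = 1000 times too low. That it excludes nobody does not depend on knowing the intended unit.

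**Retreatment reference.** There are two routes to the Second Course:

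- *Stopped after complete response:* 6.7 leads to the inclusion and exclusion criteria, and so to Table 1. Section 8.5.4 leads to 6.1, which has no limits.
- *Completed 35 cycles:* 6.6 sends these patients to 8.5.4, so their only organ-function reference is to 6.1.

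**Design figures.** Section 13.1 tests 5% against 20% in 21 patients, rejecting at 3 or more responses, "at the 8.5% level of significance and with 82.1% power". With X binomial:

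- Alpha = 1 − (0.3406 + 0.3764 + 0.1981) = 0.0849.
- Power = 1 − (0.0092 + 0.0484 + 0.1211) = 0.8213.

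Both agree with the plan, and neither uses a laboratory limit.

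**The case against.** The strongest reply is that these are clerical slips with little practical effect.

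- **Hemoglobin.** The literal *or* settles how the line operates: 8 g/dL governs. Table 1 otherwise uses conventional units, and nothing in the documents shows a site reporting hemoglobin in mmol/L. This stands. A reader might infer that eligibility turns generally on the laboratory's unit. It does not; the two halves conflict only where the mmol/L figure is used as the sole limit. But the literal reading does not show what was intended.
- **Albumin.** Most readers would silently substitute g/dL. Exclusion 5.3.18 lets the investigator exclude for a laboratory abnormality, and 8.3 requires results to be reviewed and found acceptable before each dose. These checks are real but discretionary, and they do not replace a numeric limit. A reader might say that the criterion cannot be applied. It can be applied, and everyone passes.
- **Retreatment.** The wording in 8.5.4 resembles the title of Table 1, so the intended target can be identified, and 6.7 covers patients who stopped after a complete response. This stands, and it makes the wrong reference a minor matter. Patients who completed 35 cycles still have only the wrong reference.
- **Analysis.** A reader might infer that borderline patients could change the trial's conclusion, because 13.4.2 ties the main response analysis to eligibility and the toxicity rule in 13.1 counts eligible patients. The documents give no hemoglobin or albumin distribution and no basis for such an effect. Evaluability for response in 12.1 and 13.1 rests on measurable disease, treatment received and re-evaluation, not on laboratory values.

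**Conclusion.** The point holds as an error in binding eligibility text. The hemoglobin pair differs by about 1 g/dL (0.96 to 1.24 over the assumed molar mass), or about 0.6 mmol/L. The operative limit as written is 8 g/dL. If 5.6 mmol/L was meant, patients between about 8 and 9 g/dL are admitted below the intended limit; how many cannot be said from the documents. The albumin criterion is void as written, and calling it 1000-fold too low assumes that g/dL was intended. The wrong reference in 8.5.4 is a minor related fault.

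The conclusion rests on the assumed molar mass and on serum albumin being measured in grams per dL. The text was extracted from PDF, so the albumin unit should be checked on the source page, although an inserted letter is an unlikely extraction fault. No effect is claimed on the 3-of-21 decision rule or the toxicity rule.

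**What to change.** - **Hemoglobin:** the sponsor decides which value was intended and restates the other to match. Arithmetically, 8 g/dL pairs with about 4.97 mmol/L, and 5.6 mmol/L pairs with about 9.0 g/dL. The choice is the sponsor's.
- **Albumin:** confirm the intended unit against the source and correct it so that the criterion works as a limit.
- **Checklist:** carry both corrections into the eligibility checklist required by 5.5.
- **Retreatment:** change the reference in 8.5.4 from Section 6.1 to Table 1 in 5.2.6, so that both routes to the Second Course lead to the same limits.

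The cost is three short text edits and a checklist update, with no change to sample size or analysis. If the sponsor confirms the stricter hemoglobin reading, some patients now admitted would be excluded; the documents do not allow an estimate of how many.

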	1.5 ULN
AST (SGOT) and ALT (SGPT)	≤ 2.5 X ULN OR
	\leq 5 X ULN for subjects with liver metastases
Albumin	$\geq 2.5 \text{ mg/dL}$
Coagulation	
International Normalized Ratio (INR) or	≤1.5 X ULN unless subject is receiving anticoagulant therapy
Prothrombin Time (PT)	as long as PT or PTT is within therapeutic range of intended use
	of anticoagulants
Activated Partial Thromboplastin Time	≤1.5 X ULN unless subject is receiving anticoagulant therapy
(aPTT)	as long as PT or PTT is within therapeutic range of intended use
	of anticoagulants
^a Creatinine clearance should be calculated	per institutional standard.

5.2.7. Female participants of childbearing potential must have a negative serum pregnancy within 72 hours prior to receiving the first dose of study medication). They should also be willing to use 2 methods of birth control or be surgically sterile, or abstain from heterosexual activity for the course of the study through 120 days after the last dose of study medication.

Note: Abstinence is acceptable if this is the usual lifestyle and preferred contraception for the subject.

5.2.8. Male participants must agree to use an adequate method of contraception starting with the first dose of study therapy through 120 days after the last dose of study therapy

Note: Abstinence is acceptable if this is the usual lifestyle and preferred contraception for the subject.

5.2.9. Ability to understand and willingness to sign a written informed consent and HIPAA consent document

5.3. Exclusion Criteria

- 5.3.1. Known active central nervous system (CNS) metastases and/or carcinomatous meningitis. Subjects with previously treated brain metastases may participate provided they are stable (without evidence of progression by imaging for at least four weeks prior to the first dose of trial treatment and any neurologic symptoms have returned to baseline), have no evidence of new or enlarging brain metastases, and are not using steroids for at least 7 days prior to trial treatment. This exception does not include carcinomatous meningitis which is excluded regardless of clinical stability.
- 5.3.2. Is currently participating and receiving study therapy or has participated in a study of an investigational agent and received study therapy or used an investigational device within 4 weeks of the first dose of treatment.
- 5.3.3. Diagnosis of immunodeficiency or receiving systemic steroid therapy or any other form of immunosuppressive therapy within 7 days prior to the first dose of trial treatment.
- 5.3.4. Prior anti-cancer therapy with a monoclonal antibody (mAb) within 4 weeks prior to study Day 1 or not recovered from adverse events (improved to grade 1 or less) due to mAbs administered more than 4 weeks earlier.
- 5.3.5. Prior chemotherapy, targeted small molecule therapy, or radiation therapy within 2 weeks (12 weeks for measurable sites of CNS disease) prior to study Day 1 or not recovered from adverse events (improved to grade 1 or less) due to a previously administered agent.

Note: Subjects with neuropathy or \leq Grade 2 alopecia are an exception to this criterion and may qualify for the study.

Note: If subject received major surgery, they must have recovered adequately from the toxicity and/or complications from the intervention prior to starting therapy.

- 5.3.6. Known additional malignancy that is progressing or requires active treatment except superficial malignancies of the skin and in situ cervical cancer
- 5.3.7. Has an active autoimmune disease that has required systemic treatment in the past 2 years (i.e. with use of disease modifying agents, corticosteroids or immunosuppressive drugs). Replacement therapy (e.g., thyroxine, insulin, or physiologic corticosteroid replacement therapy for adrenal or pituitary insufficiency, etc.) is not considered a form of systemic treatment.
- 5.3.8. Has history of (non-infectious) pneumonitis that required steroids, evidence of interstitial lung disease or active non-infectious pneumonitis.

- 5.3.9. Active infection requiring systemic therapy at enrollment.
- 5.3.10. Has a known history of active TB (Bacillus Tuberculosis)
- 5.3.11. Hypersensitivity to pembrolizumab or any of its excipients
- 5.3.12. Has received a live virus vaccine within 30 days of planned start of trial treatment.
- 5.3.13. Pregnant, breastfeeding, or expecting to conceive or father children within the projected duration of the trial, starting with the screening period through 120 days after the last dose of trial treatment
- 5.3.14. Prior therapy with an anti-programmed cell death 1 (PD-1), anti-programmed cell death 1 ligand (PDL-1), anti-PD-L2, or with an agent directed to another co-inhibitory T-cell receptor (e.g. CTLA-4, OX-40, CD137)
- 5.3.15. Known history of human immunodeficiency virus (HIV)
- 5.3.16. Known active Hepatitis B (e.g., HBsAg reactive) or Hepatitis C (e.g., HCV RNA [qualitative]).
- 5.3.17. Has known psychiatric or substance abuse disorders that would interfere with cooperation with the requirements of the trial
- 5.3.18. Has a history or current evidence of any condition, therapy, or laboratory abnormality that might confound the results of the trial, interfere with the subject's participation for the full duration of the trial, or is not in the best interest of the subject to participate, in the opinion of the treating investigator.

5.4. Inclusion of Women and Minorities

Men and women, regardless of race, ethnic group or sexual orientation are eligible for this study.

5.5. Patient Registration

Participants may be registered from 8:00 am to 4:00 pm EST excluding holidays by emailing the study monitor at: [contact]. Eligible participants will be entered on study centrally once the following items have been received by email:

- Completed registration form
- Consent and HIPAA signature pages
- Eligibility checklist

Following registration, participants must begin protocol treatment within 7 days of registration. Issues that would cause treatment delays must be discussed with the Principal

Copyright© 2016 Fox Chase Cancer Center[®] Clinical Trials Operations. All rights reserved.

Version Date 03/03/17

Investigator. If a registered participant does not receive protocol therapy following registration, the participant will be recorded as withdrawn from study. The Study Monitor must be notified as soon as possible if a participant does not begin protocol treatment as scheduled. For additional registration questions, please email [contact] or call [contact].

The study monitor or their designee will notify the site by email once registration is confirmed and the sequence number has been assigned. Participants must be registered and have received a sequence number prior to the initiation of treatment.

Exceptions to the current registration policies will not be permitted.

6.0 Treatment Plan

No stratification based on age, sex or other characteristics will be used in this trial. Treatment will be administered on an outpatient basis. Treatment will be administered as described below. Dose delays and modifications should only be done following protocol guidelines described in section 7.0. If treatment delays are > 42 days study therapy will be discontinued.

6.1. Trial Treatments

Agent	Dose	Route	Schedule	Cycle Length	Use
Pembrolizumab	200	IV infusion	Q 3	3 weeks (21	Experimental
	mg		weeks	days)	

6.2. Dose Selection

The rationale for selection of doses to be used in this trial is provided in Section 4.5 – Rationale.

Details on preparation and administration of pembrolizumab (MK-3475) are provided in the Pharmacy Manual.

6.3. Dose Administration

Trial treatment should be administered on Day 1 of each cycle after all procedures/ assessments have been completed as detailed on the study calendar (Section 10.0). Trial treatment may be administered up to 3 days before or after the scheduled Day 1 of each cycle due to administrative reasons. All trial treatments will be administered on an outpatient basis. Pembrolizumab will be administered as a 30 minute IV infusion (treatment cycle intervals may be increased due to toxicity as described in Section 7.0). Sites should make every effort to target infusion timing to be as close to 30 minutes as possible. However, given the variability of infusion pumps from site to site, a window of -10 minutes and +10 minutes is permitted (i.e., infusion time is 30 minutes: -10 min/+10 min).

The following infusion set materials are compatible with (pembrolizumab):

- PVC Infusion set that is plasticized using DEHP
- PVC and tri-(2-ethylhexyl) trimellitate (TOTM) infusion set
- Polyethylene lined PVC infusion set
- PVC Infusion set that is plasticized using Di-2-ethylhexyl Terephthalate (DEHT)
- Polyurethane set.

A sterile, non-pyrogenic, low-protein binding 0.2 to 5 μ m in-line filter made of polyethersulfone (PES) must be used during administration to remove any adventitious particles. If the infusion set does not contain 0.2 to 5 μ m in-line filter, it is recommended to use 0.2 to 5 μ m add-on filter which may contain an extension line. Attach the infusion line to the pump and prime the line, either with normal saline (at least 25 mL) or with infusion solution as per local SOP, before starting the infusion. Infuse pembrolizumab (MK-3475) over approximately 30 minutes, with a window of -10 and +10 minutes, through a peripheral line or indwelling catheter. Ensure the entire contents of the bag are dosed and all remaining drug solution in the line is administered according to data entry guidelines. Vital signs will be monitored every 15 minutes during the infusion and at 60 minutes after completion of each infusion. In case of infusion reactions, infusion rate may differ; refer to protocol for specific instructions.

Whenever possible, the lowest infusion rate should be used that will allow completion of the infusion within the 30 minutes. Maximum rate of infusion should not exceed 6.7 mL/min. through a peripheral line or indwelling catheter. However, when it is necessary to infuse a larger volume (i.e. 250 mL), the flow rate may go as high as 10 mL/min (maximum) in order to keep the infusion within the window as defined above

